## Protocol Synopsis

### Study Title:

An Open-Label, Single-Arm Clinical Study of ATG-010 Plus Low-Dose Dexamethasone in Patients with Relapsed/Refractory Multiple Myeloma Previously Treated with Immunomodulatory Agent and Proteasome Inhibitor

### Indication

Relapsed/Refractory Multiple Myeloma Previously Treated with Immunomodulatory Agent and Proteasome Inhibitor

### Objectives:

#### Primary Objective:

To evaluate the overall response rate (ORR) for treatment with ATG-010 plus low-dose dexamethasone in patients with relapsed/refractory multiple myeloma previously treated with immunomodulatory agent and proteasome inhibitor

#### Secondary Objectives:

To evaluate the following endpoints of ATG-010 in the study:

a. Efficacy

- Survival rate (SR) at 6 months, 9 months, and 12 months
- Time to Progression (TTP)
- Progression Free Survival (PFS)
- Duration of response (DOR)
- Clinical Benefit Rate (CBR)
- Disease Control Rate (DCR)
- Overall Survival (OS)
- Minimal Residual Disease (MRD)
- The effect of risk factor stratification on clinical efficacy

b. Safety and tolerability

c. Pharmacokinetics (PK) parameters

## Background and Study Design Rationale

### Background

Multiple myeloma (MM) is the second most common hematological malignancy (after non-Hodgkin's lymphoma), representing 1% of all cancers and 2% of all cancer deaths. According to the literature, the reported annual incidence of MM in the United States (US) and the European Union (EU) is 4.5-7/100,000. Although MM is currently not a common hematological malignancy in Asia, the incidence is rapidly increasing. In China, according to the previous epidemiology study results, the incidence of MM was 0.6/100,000 in 2005. The mortality rate of MM in China was 0.6/100,000 in 2013. In addition, another large-scale retrospective study of MM patient in China indicated that Chinese patients were often at an advanced stage with more serious renal dysfunctions and bone destructions at the time of diagnosis compared to patients in Western countries.

In the past 20 years, new therapies, such as proteasome inhibitors (PI) and immunomodulatory agents (IMiD), have significantly improved the survival rate of MM patients. Despite the increased effectiveness of variety agents in clinical practice, nearly all MM patients will eventually become

refractory to the treatment or relapse with their diseases; and their disease characteristics obviously present as drug resistance and disease progression. Therefore, there is an unmet medical need for therapies in patients with relapsed and/or refractory (RR) MM.

### **Study design rationale**

ATG-010 (Selinexor) is an orally bioavailable, selective inhibitor of nuclear export (SINE) compound that specifically blocks exportin 1 (XPO1). In preclinical studies, ATG-010 and other SINE compounds have demonstrated anti-MM activity. The completed Phase 1 clinical study, single agent ATG-010 showed an overall response rate (ORR) of 5%, while the ORR was 32% in combination with low-dose dexamethasone. In a Phase 2b clinical study (Part 1 of STORM study), the clinical efficacy and safety of ATG-010 80 mg plus dexamethasone 20 mg orally twice weekly were evaluated in patients with RRMM. The target population had either quad-relapsed/refractory MM (patients who have received bortezomib, carfilzomib, lenalidomide, and pomalidomide before enrollment) or penta-relapsed/refractory MM (patients who have received bortezomib, carfilzomib, lenalidomide, pomalidomide, and anti-CD38 monoclonal antibodies before enrollment were refractory to treatment and relapsed before enrollment). The primary endpoint for this study was ORR to validate the efficacy of the ATG-010 in these patients with polylines of relapsed/refractory disease. The preliminary results for this Phase 2b study indicated an ORR of 25.4% in the target population. Relevant results show that the efficacy of ATG-010 combined with low-dose dexamethasone is encouraging in patients with RRMM who had previously received polyline therapies and had limited treatment options.

Based on the promising efficacy data observed from the STORM study in Western population of RRMM, the current study is planned to extend ATG-010 combined with low-dose dexamethasone to the treatment of RRMM patients in China, in order to validate the clinical efficacy and safety of ATG-010 in Chinese RRMM patients.

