## Sample Size Justification

This is a bridging study. A sample size of 82 patients will allow 80% power to detect a statistical significance with the target ORR of 28% against the threshold ORR of 15% (one-sided  $\alpha=0.025$ ).

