#### 4.2.1. Efficacy Results of Study KCP-330-001

Study KCP-330-001 was a Phase I, open-label, parallel-group study, with dose escalation and dose expansion phase, to determine the MTD, to evaluate preliminary safety and efficacy of different selinexor dose schedules (3-80 mg/m^2, 1 to 3 times per week).

The results showed that, for all patients with MM (regardless of selinexor dose; n = 81), the overall response rate (ORR) was 8.6% (95%CI: 4%, 17%), including 1 patient with stringent complete response (sCR; 1.2%) and 6 patients with partial response (PR; 7.4%). The best response in another 13 patients (16%) was minimal response (MR), and the clinical benefit rate (CBR) was up to 25%. 29 patients (35.8%) had stable disease (SD), 20 (24.7%) patients had progressive disease (PD), and 1 (1.2%) patient had clinical progression.

Among the 81 selinexor-treated MM patients, 25 received selinexor (45 or 60 mg/m^2, BIW) +dexamethasone (20 mg BIW). Within these 25 patients, the ORR was 24.0% (95%CI: 9%, 45%) and CBR was 32.0%, including 1 case of sCR, 5 PRs, and 2 MRs. Eight patients (32.0%) had SD, and 5 (20.0%) patients experienced PD. All responses  $\geq$  PR occurred at the dose level of 45 mg/m^2.

selinexor.

Dose of 60 mg/m^2 was poorly tolerated and made the duration of study treatment (median, 15.0 days) shorter than that of 45 mg/m^2 (median, 110.5 days). In the 45 mg/m^2 selinexor+20 mg dexamethasone group, the median time to disease relapse or progression was 180 days. Therefore, the RP2D of selinexor in MM was 45 mg/m^2 (about 80 mg) +20 mg dexamethasone BIW.

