#### 4.2.2. Efficacy Results of Study KCP-330-012 (STORM)

STORM was a Phase 2b, open-label, single-arm study of selinexor+low-dose dexamethasone (Sd) in patients with relapsed/refractory MM. In Part 1, patients must have been previously treated with lenalidomide, pomalidomide bortezomib, and carfilzomib; and were refractory to a PI, an immunomodulatory agent (IMiD), and glucocorticoids, and a subset of the patients also were refractory to the “quad” agents (quad-refractory) as well as to an anti-CD38 antibody (i.e. penta-refractory). Patients orally took 6 or 8 doses of selinexor 80 mg (BIW) and dexamethasone 20 mg BIW in each 28-day cycle. The primary objective was to determine the ORR per International Myeloma Working Group criteria and DOR, both of which was assessed by an Independent Review Committee (IRC).

In Part 2 of the STORM study, a total of 123 patients with RRMM received selinexor 80 mg plus dexamethasone 20 mg. In the modified intent-to-treat (mITT) efficacy population, 122 patients had an ORR of 26.2%, including 2 cases of sCRs (both assessed as MRD negative), 6 VGPRs, and 24 PRs, as assessed by the IRC per IMWG criteria. The median time to initial response was 4 weeks (range: 1 to 10 weeks). The median OS was 8.6 months, 15.6 months for patients with  $\geq$  PR or  $\geq$  MR (two groups), and 1.7 months for those with PD (or NE). The PFS and OS were 4.7 and 9.3 months, respectively. Of the 32.1% (25/78 cases) patients who achieved a response  $\geq$  MR, the median OS was 11.4 months, compared to 5.8 months of those achieving SD, PD or NE.

**Table 3: Overall Response Rate Assessed by IRC per IMWG Criteria in Different Subgroups of KCP-330-012 Study (Part 2 of STORM)**

Subgroup Population (n)	Overall response rate n (%) 95%CI	Clinical Benefit Rate n (%) 95%CI
Prior anti-MM treatment		
Penta (BCLPD) refractory (n = 83)	21 (25.3) 16.4, 36.0	31 (37.3) 27.0, 48.7
Refractory to CLPD (n = 101)	26 (25.7) 17.6, 35.4	37 (36.6) 27.3, 46.8
Refractory to BCPD (n = 94)	25 (26.6) 18.0, 36.7	36 (38.3) 28.5, 48.9
Refractory to CPD (n = 117)	31 (26.5) 18.8, 35.5	45 (38.5) 29.6, 47.9
Other subgroup factors		
R-ISS stage I (n = 20)	7 (35.0) (15.4, 59.2)	10 (50.0) (27.2, 72.8)
R-ISS stage II (n = 78)	21 (26.9) (17.5, 38.2)	32 (41.0) (30.0, 52.7)
Prior anti-MM treatment		
R-ISS stage III (n = 23)	4 (17.4) (5.0, 38.8)	6 (26.1) (10.2, 48.4)
FLC MM (n = 35)	15 (42.9)	19 (54.3)

	26.3, 60.6	36.6, 71.2

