#### 13.1.2. Sample Size Determination

This trial is a bridging clinical study to evaluate the clinical efficacy of ATG-010 plus low-dose dexamethasone in Chinese patients with relapsed/refractory MM.

A sample size of 82 subjects with relapsed/refractory MM who have previously been treated with immunomodulatory agent and proteasome inhibitors (i.e., including lenalidomide and bortezomib) will allow for detecting a statistical significance of the target ORR of 28% against the threshold ORR of 15%, with power of 80% (one-sided  $\alpha=0.025$ ).

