### **13.3.3. Primary Endpoint**

The primary efficacy endpoint of ORR (proportion of patients who achieve PR, VGPR, CR, or sCR) based on mITT population and response assessment by IRC will be analyzed. For the hypothesis testing of the target ORR of 28% against the threshold ORR of 15%, a two-sided 95% confidential interval of the ORR will be provided. A lower bound of this interval >15% will indicate statistical significance of the test. ORR will also be analyzed based on the response assessments made by Investigator.

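### Is the trial underpowered because the 28% target response rate has no stated source and lies above the STORM results?

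*Combined protocol and SAP*

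**What the plan says.** Section 13.1.2 says that 82 subjects allow for "detecting a statistical significance of the target ORR of 28% against the threshold ORR of 15%, with power of 80"%, at one-sided α of 0.025. The synopsis (Sample Size Justification) says the same: "A sample size of 82 patients will allow 80% power to detect a statistical significance with the target ORR of 28"%. Both call the trial a bridging study, and neither says where 28% comes from.

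The success rule is in section 13.3.3. A two-sided 95% interval for the ORR is computed, and "A lower bound of this interval >15% will indicate statistical significance of the test". The interval method is not named.

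The earlier results appear in several places:

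- **STORM, synopsis (Study design rationale):** "The preliminary results for this Phase 2b study indicated an ORR of 25.4% in the target population". The trial is then tied to that study: "Based on the promising efficacy data observed from the STORM study in Western population of RRMM, the current study is planned".
- **STORM Part 2, section 4.2.2:** "122 patients had an ORR of 26.2%, including 2 cases of sCRs (both assessed as MRD negative), 6 VGPRs, and 24 PRs".
- **Phase 1, synopsis:** "single agent ATG-010 showed an overall response rate (ORR) of 5%, while the ORR was 32% in combination with low-dose dexamethasone", with no numerator, denominator or dose.
- **Phase 1, section 4.2.1, 25 patients on the combination:** "the ORR was 24.0% (95%CI: 9%, 45%) and CBR was 32.0%, including 1 case of sCR, 5 PRs, and 2 MRs". All responses of PR or better were at 45 mg/m²; the size of that dose group is not given.

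On population, section 5 says the design starts from lenalidomide and bortezomib as the initial treatment option and describes the target patients as second-line refractory. Inclusion criterion 3 (section 8.2) requires refractoriness to those two drugs, and refractoriness or intolerance to the latest line.

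**The concern.** The trial has one primary test, and its stated power is a statement about a true ORR of 28%. A reader looking for the origin of that figure finds none. The study is presented as an extension of STORM, yet both STORM rates fall below the target. The only whole-cohort combination rate above it is the 32% in the synopsis, which section 4.2.1 does not bear out: there the combination ORR is 24.0%, and 32.0% is the clinical benefit rate (and also the stable disease rate). With 24.0% in place of 32%, every whole-cohort combination ORR in the document is below 28%.

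If Chinese patients responded just as STORM's did, the chance of missing the pass mark would be 31% to 38%, where a reader of section 13.1.2 expects 20%. A trial could then miss while the drug performed as it had before. That would argue for a larger sample, or at least for a stated justification of the target.

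**Working it through.** **Inputs.** n = 82, null rate 0.15, target 0.28, one-sided α = 0.025 (section 13.1.2); success if the lower 95% bound exceeds 15% (section 13.3.3). Because the interval is not named, the exact (Clopper-Pearson) interval is assumed; it reproduces the stated power.

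**Step 1: the plan's own figure.** The exact lower bound for x responders is the 0.025 quantile of Beta(x, 82 − x + 1).

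- x = 19: 14.56%, fail.
- x = 20: 15.58%, pass.

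The pass mark is 20 responders (20/82 = 24.4%). Then:

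- P(X ≥ 20 | 82, 0.15) = 0.0172, within 0.025.
- P(X ≥ 20 | 82, 0.28) = 0.8012.

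The stated 80% is right. In addition, 82 is the smallest n from which exact power stays at or above 80%.

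**Step 2: same design, other true rates.**

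| True ORR | Where it is printed | Exact interval, pass mark 20 | Wilson interval, pass mark 19 |
|---|---|---|---|
| 24.0% | section 4.2.1 | 51.0% | 61.2% |
| 25.4% | synopsis, preliminary | 62.5% | 71.8% |
| 26.2% | section 4.2.2 | 68.5% | 77.0% |
| 28.0% | section 13.1.2 | 80.1% | 86.5% |
| 32.0% | synopsis, Phase 1 | 94.8% | 97.0% |

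Wilson's one-sided error at 15% is 0.0328, above 0.025, so it is not the reading that matches the plan. Under the exact rule the miss probability is 1 − 0.685 = 31.5% at 26.2% and 1 − 0.625 = 37.5% at 25.4%. Exact power would stay at or above 80% from n = 113 at 26.2% and n = 125 at 25.4%.

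**Step 3: how far 28% is from STORM.** 2 + 6 + 24 = 32 responders, and 32/122 = 26.2%, with exact 95% interval 18.7% to 35.0%. The target is 28.0 − 26.2 = 1.8 points higher and well inside the interval. If half of the 82 patients responded at 26.2%, the other half would need (28.0 − 0.5 × 26.2)/0.5 = 29.8% to give 28% overall.

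**Step 4: whether the populations are the same.** Section 1 describes the STORM patients behind the FDA approval as refractory to five agents. In Table 3, 83 of the 122 Part 2 patients (83/122 = 68%) were penta-refractory, and 117 (117/122 = 96%) were refractory to carfilzomib, pomalidomide and daratumumab together. The present trial requires refractoriness to two named drugs. A planning rate slightly above STORM's is consistent with that difference.

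**Step 5: the Phase 1 figures.** 1 sCR + 5 PR = 6, and 6/25 = 24.0%. Adding 2 MR gives 8/25 = 32.0%, the clinical benefit rate. The 25 patients pool two dose levels, with every responder at 45 mg/m², the level that section 5.1 equates to about 80 mg. The rate at that level is therefore at least 24.0%. It would exceed 28% if the group had 21 or fewer patients (6/21 = 28.6%), and would round to 32% with 19 (6/19 = 31.6%). Neither a dose subgroup nor a benefit rate printed as an ORR can be confirmed from the documents. The synopsis's 5% for the single agent is likewise untraced: section 4.2.1 implies (7 − 6)/(81 − 25) = 1/56 = 1.8%.

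**The case for a change.** The best case for acting is that power hangs on an assumption the sample-size text does not defend. The population argument is available in section 5 and the entry criteria, but section 13.1.2 does not make it and gives no assumed prior-treatment mix. Section 13.1.1 plans an interim look to learn that mix. The synopsis also says that Chinese patients often present at a more advanced stage, so a higher rate is not self-evident. STORM's interval extends below 26.2% as well as above it: averaged over the uncertainty in 32/122 (Jeffreys prior, Beta(32.5, 90.5)), power is about 65%. One or two sentences would settle the matter.

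The facts in that case stand: no source is given, and exact power at 26.2% is about 69%. Three things limit their force. First, power of 62% to 69% answers a different question from the one section 13.1.2 answers; the plan claims 80% at 28%, and that is true. Second, the lower end is weak. The 25.4% is preliminary and printed without a numerator or denominator. It also equals 31/122, so it may be an earlier cut of the same patients, though that is inference. The 24.0% pools two dose levels. Third, averaging over STORM's uncertainty treats STORM's patients as exchangeable with this trial's, which the entry criteria do not support.

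**Conclusion.** No change follows. The sample-size statement is correct for the design it describes: 82 patients, pass mark 20, exact power 80.1% at 28%, one-sided error 0.0172. The target is a reasonable alternative, 1.8 points above the 26.2% of a more refractory population and within that estimate's 95% interval. It plays no part in the success rule, the interval or the error rate, so citing its source would leave every result as it is. Re-sizing to 113 or 125 would buy power at rates the plan does not assume, at a cost of 31 to 43 more patients (113 − 82 and 125 − 82), when no stated figure has been missed.

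Two documentation gaps remain: the uncited 28%, and the synopsis's Phase 1 ORR of 32% against 24.0% in section 4.2.1. The second is background text, and nothing in the documents shows that it fed into the design. Anyone interpreting a near miss should know that power is about 69% at STORM's rate.

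This rests on the exact interval being the one used, and on the trial enrolling the less refractory population its entry criteria describe. If the sponsor's real expectation were STORM's rate, accepting about 69% power would be a trade-off for the sponsor to weigh and would still not be an error in the plan.

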### **Study Design**

This is a single-arm and open-label study. Approximately 82 patients will be enrolled in the study. The treatment regimen is ATG-010 80 mg plus dexamethasone 20 mg by oral, twice per week, 4 weeks per cycle. Clinical efficacy, safety and tolerability of ATG-010 will be evaluated. Blood samples from the 15 patients of enrolled will be collected for additional PK analysis.

### **Study Population**

#### **Inclusion Criteria:**

Patients must meet all of the following inclusion criteria to be eligible to enroll in this study:

1. Aware and sign the informed consent form (ICF) voluntarily.
2. Age  $\geq$  18 years.
3. Patients with multiple myeloma must have previously received regimens with immunomodulatory agent (lenalidomide) and proteasome inhibitor (bortezomib), are refractory to both drugs, and are refractory or intolerant to the most recent line of therapy (Patients documented as intolerant are allowed to be screened only after discussing and obtaining an approval from Sponsor Medical Monitor). Refractory MM includes primary refractory (patients do not achieve minimal response (MR) or have disease progression during therapy) or secondary refractory patients have progression within 60 days after completion of therapy).

4. Any non-hematological toxicities (except for peripheral neuropathy as described in exclusion criterion #17) that are relevant to previous therapies must have resolved to  $\leq$  Grade 2 prior to the first dose of study drug.
5. Adequate hepatic function: total bilirubin  $<2\times$  upper limit of normal (ULN) (for patients with Gilbert's syndrome, a total bilirubin of  $<3\times$  ULN is required), AST  $<2.5\times$  ULN, and ALT  $<2.5\times$  ULN.
6. Adequate renal function: estimated creatinine clearance  $\geq 20$  mL/min (calculated using the formula of Cockroft-Gault).
7. Eastern Cooperative Oncology Group (ECOG) Performance Status of 0, 1, or 2.
8. Measurable MM as defined by at least one of the following:
  - a. Serum M-protein (by serum protein electrophoresis, SPEP)  $\geq 5$  g/L,
  - b. 24 hours-Urinary M-protein excretion  $\geq 0.2$  g (200 mg),
  - c. Serum free light chain (FLC)  $\geq 100$  mg/L with abnormal FLC ratio.
9. Adequate hematopoietic function (no platelet transfusions within 1 week, and no red blood cell transfusions within 2 weeks prior to screening examination):
  - a. Hemoglobin level  $\geq 80$  g/L
  - b. ANC  $\geq 1000/\text{mm}^3$  ( $1.0\times 10^9/\text{L}$ )
  - c. Percentage of plasma cells in bone marrow  $<50\%$ , platelet count  $\geq 75,000/\text{mm}^3$  ( $75\times 10^9/\text{L}$ ); or percentage of plasma cells in bone marrow  $\geq 50\%$ , platelet count  $\geq 50,000/\text{mm}^3$  ( $50\times 10^9/\text{L}$ ).
10. Female patients of childbearing potential must meet below two criteria:
  - a. Female patients of childbearing potential must agree to use 2 methods of contraception acceptable by the study physician or complete sexual abstinence throughout the study, and for 3 months following the last dose of study treatment.
    - i. Sexual abstinence: this method is acceptable when it is consistent with the patient's preference and daily lifestyle. Periodic abstinence (based on calendar, ovulation, symptomatic body temperature, or post-ovulation methods) is not acceptable.
    - ii. Acceptable contraception methods include: oral contraceptives, injectable contraceptives, or implanted sex hormonal contraceptives, intrauterine contraceptive device, barrier contraceptives with spermicide; or a sexual partner who is status post of a sterilization surgery and using at least one barrier contraceptive tool.
  - b. Must have a negative serum pregnancy test at screening.

Note: Female patients of childbearing potential refer to all women who have started menarche and are not in the postmenopausal period and have not had surgical sterilization (for example hysterectomy, bilateral salpingectomy, and bilateral oophorectomy). Postmenopausal is defined as more than 12 consecutive months of amenorrhea for unspecified reasons. Women who are taking oral contraceptives or using mechanical contraceptive method such as intrauterine device are considered childbearing potential.
11. Male patients (including those who have received vasectomy) must agree to use a condom if sexually active with a female of child-bearing potential from the date of signing the informed consent form (ICF), throughout the study, and for 3 months without pregnancy plan following the last dose of study treatment.

#### **Exclusion Criteria:**

Patients who meet any of the following criteria will not be enrolled:

1. Asymptomatic (smoldering) MM.
2. Plasma cell leukemia.
3. Documented complicated with amyloidosis.
4. Central nervous system (CNS) involved MM.
5. Pregnancy or breastfeeding.
6. Prior to the first dose of study drug:
  - a. Chemotherapy within 1 week (including steroid therapy in chemotherapy regimen);
  - b. Radiation, immunotherapy or other anti-MM therapy within 4 weeks;
  - c. Radio-immunotherapy within 6 weeks.
7. Graft versus host disease (after allogeneic stem cell transplantation).
8. Life expectancy of < 4 months.
9. Major surgery within 4 weeks prior to the first dose of study drug.
10. Patients with active, unstable cardiovascular diseases, meet any of the following:
  - a. Symptomatic ischemia;
  - b. Uncontrolled clinically-significant conduction abnormalities (e.g., patients with ventricular tachycardia on antiarrhythmics are excluded; patients with first-degree atrioventricular (AV) block or asymptomatic left anterior fascicular block/right bundle branch block (LAFB/RBBB) are allowed);
  - c. Congestive heart failure (CHF) of New York Heart Association (NYHA)  $\geq$  Grade 3;
  - d. Acute myocardial infarction (AMI) within 3 months prior to the first dose of study drug.
11. Uncontrolled hypertension (systolic blood pressure  $>140$  mmHg or diastolic blood pressure  $>90$  mmHg).
12. Uncontrolled active infection requiring treatment within 1 week prior to the first dose of study drug.
13. Known HIV seropositive.
14. Known active hepatitis A, B, or C infection; or known to be positive for HCV RNA or HBsAg (HBV surface antigen).

Note: including HBsAg negative but hepatitis B cored (HBc) antibody positive with detectable hepatitis B virus deoxyribonucleic acid (HBV-DNA) level (the upper limit of normal for HBV-DNA testing is based on the test value of each center).
15. Prior malignancy that required treatment or has shown evidence of recurrence (except for skin basal-cell carcinoma and the following in-situ carcinoma: squamous cell carcinoma, bladder cancer in situ, endometrial cancer in situ, cervical cancer in situ/atypical hyperplasia, accidental histological finding of prostate cancer (TNM staging is T1a or T1b), or breast cancer in situ) within 5 years prior to the first dose of study drug.
16. Active GI dysfunction interfering with the ability to swallow tablets, or any GI dysfunction that could interfere with absorption of study treatment.
17. Grade  $\geq 3$  peripheral neuropathy, and Grade  $\geq 2$  painful neuropathy, within 3 weeks prior to the first dose of study drug.
18. Active psychiatric disorder, or organic disease which, in the opinion of the Investigator, is not suitable for the study.
19. Participation in another investigational anti-cancer clinical trial within 3 weeks or within 5

half-life ( $T_{1/2}$ ) time periods prior to the first dose of study drug.

20. Receipt any following treatments prior to the first dose of study drug:

- Platelet infusion within 1 week;
- RBC transfusion within 2 weeks;
- Receipt of the following blood growth factors within 2 weeks: Granulocyte colony stimulating factor (G-CSF), granulocyte-macrophage colony stimulating factor (GM-CSF), erythropoietin (EPO), megakaryocyte growth factor, and/or platelet stimulating factor.

21. Known intolerance to or contraindication for glucocorticoid therapy.

22. Prior exposure to a SINE compound, including ATG-010.

